**12-Month Post-Implementation Assessment Procedures:**

Administrative, Behavioral, and Regulatory Procedures

- Quantitative questionnaire via Qualtrics
  - To assess HIV test site characteristics (site demographics and site context)
  - To assess acceptability of the intervention

**24-Month Post-Implementation Assessment Procedures:**

Administrative, Behavioral, and Regulatory Procedures

- Quantitative questionnaire via Qualtrics
  - To assess HIV test site characteristics (site demographics and site context)
  - To assess acceptability of the intervention

**Post-24-Month Assessment Qualitative Interview Procedures [among site staff (n=12), site directors (n=12) and HIV providers (n=12) at 12 selected sites] (see Section 5.4.1):**

Administrative, Behavioral, and Regulatory Procedures

- Informed consent to participate in qualitative in-depth interview
- Qualitative in-depth interview

**6-10 Months Post-endline Assessment Procedures (see Section 5.4.1):**

Administrative, Behavioral, and Regulatory Procedures

- Informed consent to participate in PRESS survey
- PRESS survey

Administrative, Behavioral, and Regulatory Procedures [among site navigators/counselors ( $n=12$ ), site directors/staff ( $n=24$ ) at 12 selected sites] (see **Section 5.4.1**):

- Informed consent to participate in qualitative in-depth interview
- Qualitative in-depth interview

## 5.6. Study Procedures for System Navigators and Counselors at Sites

Navigators and counselors are part of the Site Staff and, if they consent, they will participate in the visit procedures for Site Directors and Staff in Section 5.5.2.

Separately, as part of their work as site staff navigators/counselors at the HIV test site, at each navigator and counselor session, navigators and counselors will complete the following:

- **Maintain a log of PWID engaged in their care.**
  - This log will capture, in a simple format, the PWID's name, medical record number, and the type of encounter.
- After each navigation or counseling session, **complete a brief encounter form**, based on those used in HPTN 074:
  - The ***navigation form*** will capture the mode of communication (in-person, telephone, SMS text), ART/MAT status, availability of a social support person, duration of the encounter, and encounter content (HIV care, ART, MAT, sexual health, etc.).
  - The ***counseling form*** will capture the type of session (initial or booster), availability of social support, session focus, barriers addressed, duration, and need for systems navigation.
  - These forms will be forwarded monthly to the Hanoi study site for data entry.
- **All counseling sessions will also be audio-recorded** and reviewed periodically by site supervisors to provide feedback to counselors, as a standard procedure. Consent for audio-recording will be obtained from the study participant.

### 5.6.1 **Quality of navigation sessions**

The quality of navigation sessions will be measured by rating the navigator encounter forms. For each site, the central implementation teams will review the first 10 navigation encounter forms and a randomly selected 50% of all remaining navigation encounter forms, and rate each encounter on a 5-point quality scale from poor to excellent.

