### 5.6.2 **Quality of counseling sessions**

For each site, the central implementation teams will also review the first 5 counseling session audio-recordings and a randomly selected 50% of all remaining counseling session audio-recordings and rate each on a 10-point quality scale.

For central review of recordings, identifying information of the PWID will not be provided to the central team. The quality rating forms and recordings will be forwarded monthly to the Hanoi team.

Navigators/counselors will be compensated for time as *Site Staff study participants at study visits* (Section 5.5.2), such as for their time answering study questionnaires

and in-depth interviews. However, as an implementation study, navigators/counselors will not be compensated *by the study* for their work as navigators/counselors at each HIV test site, as their work delivering the SNaP intervention will be run by the HIV test site.

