### 7.2. Implementation Outcomes (Aim 1)

#### 7.2.1 Primary Implementation Outcome

The primary implementation outcome will be fidelity to SNaP intervention procedures (**Table 2**). Fidelity is measured as follows:

$$\text{Fidelity} = (\% \text{ navigation sessions completed} * \% \text{ quality score} + \% \text{ counseling sessions completed} * \% \text{ quality score})$$

Fidelity will be measured at the test site level by assessing each site's success in completing the three protocol-specified sessions (two navigation, one counseling) within the required eight- or four-week period, respectively, weighted by the central implementation team's quality rating of those sessions. Session completion will be assessed by reviewing the navigator and counselor logs, while session quality will be

assessed by central implementation team review and scoring of the first 10 and 5 of all forms (navigation) and audio-recordings (psychosocial counseling) respectively and a random 50% of all remaining forms and audio-recordings at each site, as described in Section 5.6 above. Reviewers will be masked to the arm when reviewing navigation forms or audio-recordings. For context, in HPTN 074, the Vietnam site achieved >85% completion of the 4 sessions in the protocol-specified windows, showing that in the context of a carefully monitored trial, high completion of appointments within an eight-(SN) or four-week (PC) window by this population is feasible.

The test site fidelity score will range from 0-200. The score will be the percentage of expected navigation sessions that are completed, multiplied (weighted) by the average quality rating of navigation sessions; plus the percentage of expected counseling sessions that are completed, multiplied by the average quality rating of counseling sessions. Thus, a site completing all navigation sessions with a perfect quality rating (100 points) and all counseling sessions with a perfect rating (100 points) would receive the maximum fidelity score of 200 points, whereas a site completing 90% of navigation sessions with an 80% average quality score ( $100*0.9*0.8 = 72$  points) and 80% of counseling sessions with an 80% average quality score ( $100*0.8*0.8 = 64$  points) would receive a total score of  $72 + 64 = 136$  points.

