**Table 2. Study Outcomes**

Outcome	Definition	Measure or Scale*
Primary Integration Implementation Outcome		
Fidelity to SNaP protocol	Delivering SNaP as intended.	(systems navigation % * average quality score) + (counseling session % * average quality score) [see text for example]
Secondary SNaP Implementation Outcomes		
Penetration	% of PWID contacted, & enrolled in SNaP	Proportion of newly diagnosed or previously diagnosed and not currently on ART PWID at test sites who are contacted by a navigator and/or counselor and participate in a SNaP session.
Acceptability	Perception that SNaP is agreeable, palatable, or satisfactory.	OADRI (adapted): 12-item scale, staff and client acceptability of an innovation in a clinic setting.  and qualitative interviews
Implementation costs	Costs of SNaP & its implementation	Directly measured non-research costs (Aim 2)
Primary Effectiveness Outcome		
Uptake of ART	% PWID who initiated ART	ART clinic records of consenting PWID
Secondary Effectiveness Outcomes		
Viral suppression	% PWID virally suppressed	Undetectable viral load on DBS**, in PWID subsample cohort
Uptake of MAT	% of PWID on MAT	MAT clinic records of consenting PWID

\*All measures will be adapted to SNaP; \*\*DBS=dried blood spot

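### Early sessions are all rated and later ones at 50%, but the fidelity score uses an average quality rating with no selection weights

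*Combined protocol and SAP*

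**What the plan says.** For navigation, Section 5.6.1 has the central implementation teams, at each site, "will review the first 10 navigation encounter forms and a randomly selected 50% of all remaining navigation encounter forms". For counseling, Section 5.6.2 says they "will also review the first 5 counseling session audio-recordings and a randomly selected 50% of all remaining counseling session audio-recordings". Section 7.2.1 repeats both rules.

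Section 7.2.1 then builds the site score: "The score will be the percentage of expected navigation sessions that are completed, multiplied (weighted) by the average quality rating of navigation sessions". The counseling half is formed the same way, with completion "multiplied by the average quality rating of counseling sessions". Table 2 gives the same formula. The word in brackets in the navigation sentence describes multiplying completion by quality. It does not refer to how sessions were selected for rating.

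No section states selection weights, and none separates early from later ratings. The model in Section 8.2.1 compares mean site scores and does not address the point either. Section 8.1.1 makes the test site the unit of analysis, with 21 sites per arm. Sections 5.4 and 7.5 use a score of 136 as the fidelity part of the definition of a successful site.

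**The concern.** The quantity wanted is the average quality of the sessions a site delivered. The rated sessions are not an equal-probability sample of them: early sessions enter with probability 1 and later ones with probability 0.5. A plain mean of the ratings therefore gives each early session twice the influence of a later one. It misstates the site's average whenever early and later quality differ.

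The size of the distortion depends on how many sessions a site delivers, and Section 8.1.2 puts site size between 7 and 764 PWID. Each site counts once in the fidelity comparison, so the mean-sized site does not show the full effect. What is at stake is the accuracy of individual site scores for a primary outcome, and the classification of sites near 136, which feeds the selection of interview sites and the Aim 3 models.

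**Working it through.** **Inputs from the documents.** First 10 forms and first 5 recordings rated with certainty, the rest at 50% (5.6.1, 5.6.2, 7.2.1). Two navigation sessions and one counseling session specified per participant (7.2.1). Site size 7 to 764 PWID, mean about 148 (8.1.2). 21 sites per arm; 136 vs 100.5 at SD 40, and 136 vs 111 at SD 28 (8.1.1).

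**Assumptions.** Completion of 80%, the value Section 8.1.1 expects TA to reach or exceed. Only protocol-specified sessions are rated. Gap between early and later quality of 5 to 20 points, sign unknown.

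**Step 1: the plan's own figures.** A two-sided two-sample t-test at 0.05 with 21 sites per arm gives 80.1% power for 35.5 points at SD 40 and 80.6% for 25 points at SD 28. Both agree with the stated 80%. The scores also reproduce: 200 × 0.80 × 0.85 = 136, 200 × 0.75 × 0.67 = 100.5 and 200 × 0.75 × 0.74 = 111. These figures do not depend on the weighting question.

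**Step 2: share of early sessions.** With N sessions completed and the first k all rated:

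- share of sessions delivered = k/N
- share of a plain mean of ratings = k/(k + 0.5(N − k))

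For navigation, k = 10 and N = 2 × PWID × 0.8. For counseling, k = 5 and N = PWID × 0.8. Both k and N halve, so the shares are the same. Example at 30 PWID: N = 48, so 10/48 = 20.8% of sessions; rated sessions are 10 + 19 = 29, so 10/29 = 34.5% of the average.

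**Step 3: shift in the 0-200 score.** Shift = 0.8 × (excess share, navigation + excess share, counseling) × gap. Example at 30 PWID with a gap of 20: 0.8 × (0.136 + 0.136) × 20 ≈ 4.4.

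| PWID at site | Share of sessions | Share of plain mean | Excess (points) | Shift, gap 5 | Shift, gap 20 |
|---|---|---|---|---|---|
| 7 | 89.3% | 94.3% | 5.1 | 0.4 | 1.6 |
| 15 | 41.7% | 58.8% | 17.2 | 1.4 | 5.5 |
| 30 | 20.8% | 34.5% | 13.6 | 1.1 | 4.4 |
| 148 | 4.2% | 8.1% | 3.9 | 0.3 | 1.2 |
| 764 | 0.8% | 1.6% | 0.8 | 0.1 | 0.3 |

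The excess is largest at about 24 navigation or 12 counseling sessions. That is 15 PWID at 80% completion and 12 PWID at full completion. It is zero where a site has no more than 10 forms or 5 recordings.

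**Step 4: the cut-off.** A 30-PWID site with 80% completion and a true average quality of 85% has a true score of 136. If its early sessions rate 10 to 20 points lower than later ones, the plain mean puts it at 136 − 2.2 = 133.8 down to 136 − 4.4 = 131.6, and it misses the cut-off. If early sessions rate higher, a site slightly below 136 is lifted over it.

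**Step 5: does weighting repair it?** A simulation of navigation ratings with assumed quality of 65% early and 85% later, all sessions completed, gave at 12 PWID a true mean of 76.7%, a plain mean of 73.2% and a weighted mean of 76.7%. At 148 PWID the three values were 84.3%, 83.7% and 84.3%.

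**The case against.** The plan says average and is silent on weights. A weighted mean also estimates that average, so the plain mean is a natural reading and not a declared choice. This stands, and it is why the point asks for a statement of method. But an analyst following the text would most likely take the simple mean, so the silence is worth closing.

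The number of rated forms may be larger than assumed, because Section 5.6 calls for a form after every session and Section 4.1 allows further navigation and booster counseling. If the count doubled, the excess at 30 PWID would be 10/53 − 10/96 = 8.5 points and the 20-point shift about 2.7. At the very smallest sites the excess can rise instead. This also stands.

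Three stronger readings are tempting, and the documents do not support them.

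- **That start-up sessions distort the scores.** Recruitment runs 21 months. With even accrual, the first 10 forms span 10 ÷ (2 × PWID × 0.8 / 21) months: about 9 at 15 PWID, 4.4 at 30 and 0.9 at 148. Where the over-weighting is large, the early sessions are mostly not start-up. Nothing in the documents says early sessions rate lower, and quality could equally drift down later.
- **That the primary comparison is biased or underpowered.** The rule is the same in both arms, randomization is stratified by size (5.1.4) and reviewers are masked to arm (7.2.1). The contrast is biased only if the early-later gap differs by arm. TA's monthly calls make that plausible, but it is not shown. One can force a loss by assuming that TA has no quality advantage at all in early sessions and by assuming a distribution of site sizes: 25 points falls to 23.5-23.9 and power to 76-77%. But TA sites complete their site assessment before implementation and receive site-specific training (4.2.2, 5.1.6), so that case is extreme.
- **That the smallest sites are hit hardest.** The excess peaks near 12-15 PWID and is lower below that.

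**Conclusion.** The point holds as an estimator problem of modest size. Under the stated sampling rule, an unweighted average does not estimate a site's average session quality unless early and later quality are equal. The shares follow from the documents' own sampling rule, with 80% completion and only protocol-specified sessions rated. The score shifts rest on an assumed gap of 5 to 20 quality points in either direction: about 1.1 to 4.4 points at 30 PWID and 0.3 to 1.2 at 148. How many sites lie near 15-30 PWID is unknown, since the documents give only the range and the mean.

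Against detectable differences of 25 to 35.5 points this is minor, and the stated power is not in question. The practical consequence is for individual site scores, above all for sites close to 136. It is a worthwhile improvement, and the trial's main conclusion is not shown to depend on it.

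**What to change.** In Section 7.2.1, define each site's navigation quality and counseling quality as weighted means of the rated sessions. Give weight 1 to the first 10 forms or first 5 recordings. Give every later rated session the inverse of the sampling fraction achieved at that site, which is about 2. Say also whether extra navigation sessions and booster counseling sessions belong to the set being averaged.

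The cost is one sentence in the plan and one line of code, with no additional ratings. The downside is slightly higher sampling variance. At 30 PWID, with 10 early and 19 later navigation ratings of equal variance, the effective number of ratings is (10 + 2 × 19)² / (10 + 4 × 19) = 2304/86 ≈ 26.8 instead of 29, so the variance of that site's navigation quality rises by about 8%.

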### 5.6.2 **Quality of counseling sessions**

For each site, the central implementation teams will also review the first 5 counseling session audio-recordings and a randomly selected 50% of all remaining counseling session audio-recordings and rate each on a 10-point quality scale.

For central review of recordings, identifying information of the PWID will not be provided to the central team. The quality rating forms and recordings will be forwarded monthly to the Hanoi team.

Navigators/counselors will be compensated for time as *Site Staff study participants at study visits* (Section 5.5.2), such as for their time answering study questionnaires

and in-depth interviews. However, as an implementation study, navigators/counselors will not be compensated *by the study* for their work as navigators/counselors at each HIV test site, as their work delivering the SNaP intervention will be run by the HIV test site.

## 6. SAFETY MONITORING AND ADVERSE EVENT (AE) REPORTING

### 6.1. Safety Monitoring

The study will be monitored through close collaboration of the study principal investigators, implementing sites, Vietnam collaborators, and the appropriate institutional review boards. Particular care is given due to the high-risk nature of this study population.

At each contact with PWID and HIV test site directors and staff, the study team will ask about any social harms experienced as a result of study. We will also provide all participants with study contact information and ask that they contact us immediately if they experience any social harm or other adverse event, such as disruption of families, acts of discrimination or physical harm. Study staff will refer people to appropriate care should an adverse event come to our attention that needs professional or medical intervention. If a social harm is reported, a short questionnaire will be administered to characterize the social harm and describe its impact. All reported social harms will be documented and communicated to the HMU IRB and the UNC IRB within 7 days.

We will establish a safety monitoring committee (SMC) comprising at least three people. The SMC will meet at the outset of the study in person then semi-annually by telephone or in person. The semi-annual SMC meeting will assess whether study objectives are being met and will ensure that benefit exceeds harm. The SMC will review the protocol, assessments, and consent forms prior to study initiation. The SMC will receive all reports of AEs at the same time that the AEs are forwarded to the HMU and UNC IRBs. Severe AEs will trigger an immediate meeting of the SMC. Additional meetings of the SMC can be scheduled, as needed, to discuss and resolve AE issues. Members of the SMC will include representatives of the government sponsored HIV test sites, an infectious disease physician, epidemiologist or other expert, and a methodologist. The SMC will submit minutes following every meeting to UNC IRB and the HMU IRB.

### 6.2. Adverse Event Reporting

Non-serious adverse events will be collected and recorded in the source documentation with referrals as necessary, but not reported in the database as part of this research protocol for all study participants. Non-serious adverse events will be collated and reported to the SMC for each SMC meeting. This report will be shared with the appropriate institutional review boards.

Serious AEs (SAEs) are defined per International Conference on Harmonisation (ICH) guidance and will be collected and reported on case report forms (CRFs) for all study participants. Only SAEs leading to death, life threatening SAEs and suspected unexpected serious adverse events (SUSAEs) will be reported to the PIs within 24 hours of the study site learning of the SAE, and reported to the SMC within 72 hours and the appropriate institutional review boards within 7 days from the time site staff learned of the SAE. Other SAEs will follow the reporting of non-serious adverse events.

### 6.3. Social Impact Reporting

It is possible that participants' involvement in the study could become known to others, and that a social impact may result (i.e., because participants could be perceived as being HIV-infected

or at risk or "high risk" for HIV infection). For example, participants could be treated unfairly, or could have problems being accepted by their families and/or communities. A social impact that is reported by the participant and judged by the PIs to be expected or not. If a social impact is not unexpected, site staff will complete a detailed description of the impact using the UNC IRB's New Safety Information. This report will be reported to the SMC within 72 hours and the appropriate institutional review boards within 7 days from the time site staff learned of the unexpected social impact.

Given the status of illegal drug use, the associated social stigma and perceptions of drug users held by many members of the communities in which the study will be conducted, social harms could occur purely as a result of participation in a study targeting drug users. These could include discriminatory treatment and violence associated with possible disclosure of participants' drug or sex-related behaviors or of their HIV serostatus.

## 7. STUDY ASSESSMENTS AND OUTCOMES

### 7.1. Site-level Assessments

**To assess the site characteristics**, we will ask test sites (site directors and staff) to provide information at the start of the study (i.e., at baseline, pre-implementation), and at 12- and 24-months post-implementation on the following site characteristics:

Site demographic characteristics (in the past 1 month):

- a. Number of HIV tests performed
- b. PWID size (number of HIV tests performed who are PWID)
- c. PWID proportion (number of PWID over total tests performed)
- d. Sex distribution (men and women who are PWID)

Site context characteristic measures (**Table 1**):

- a. Organizational readiness to change – ORIC scale
- b. Implementation leadership – Implementation Leadership Scale
- c. Implementation climate – Implementation Climate Scale

### 7.2. Implementation Outcomes (Aim 1)

#### 7.2.1 Primary Implementation Outcome

The primary implementation outcome will be fidelity to SNaP intervention procedures (**Table 2**). Fidelity is measured as follows:

$$\text{Fidelity} = (\% \text{ navigation sessions completed} * \% \text{ quality score} + \% \text{ counseling sessions completed} * \% \text{ quality score})$$

Fidelity will be measured at the test site level by assessing each site's success in completing the three protocol-specified sessions (two navigation, one counseling) within the required eight- or four-week period, respectively, weighted by the central implementation team's quality rating of those sessions. Session completion will be assessed by reviewing the navigator and counselor logs, while session quality will be

assessed by central implementation team review and scoring of the first 10 and 5 of all forms (navigation) and audio-recordings (psychosocial counseling) respectively and a random 50% of all remaining forms and audio-recordings at each site, as described in Section 5.6 above. Reviewers will be masked to the arm when reviewing navigation forms or audio-recordings. For context, in HPTN 074, the Vietnam site achieved >85% completion of the 4 sessions in the protocol-specified windows, showing that in the context of a carefully monitored trial, high completion of appointments within an eight-(SN) or four-week (PC) window by this population is feasible.

The test site fidelity score will range from 0-200. The score will be the percentage of expected navigation sessions that are completed, multiplied (weighted) by the average quality rating of navigation sessions; plus the percentage of expected counseling sessions that are completed, multiplied by the average quality rating of counseling sessions. Thus, a site completing all navigation sessions with a perfect quality rating (100 points) and all counseling sessions with a perfect rating (100 points) would receive the maximum fidelity score of 200 points, whereas a site completing 90% of navigation sessions with an 80% average quality score ( $100*0.9*0.8 = 72$  points) and 80% of counseling sessions with an 80% average quality score ( $100*0.8*0.8 = 64$  points) would receive a total score of  $72 + 64 = 136$  points.

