### **Central Implementation Teams:**

A central implementation team will be used to conduct the Intervention Mapping that occurs *prior to randomization* (Figure 1).

After randomization, two central implementation teams (one for each arm) will facilitate study implementation. Implementation will be done for both arms simultaneously in a rolling process, working systematically through the regions of Vietnam.

Central implementation teams will have separate group calls with the SA and TA test sites every 6 months to share experiences and lessons learned.

Each central implementation team will comprise:

- 1) A UNC-Vietnam Hanoi staff member,
- 2) A VAAC representative, and
- 3) A Hanoi Medical University (HMU) representative.

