#### **5.1.6 Trainings**

- Selection and training of navigators and counselors:

We will train existing HIV test site staff, selected by test site directors, to become systems navigators and psychosocial counselors for SNaP. Test sites will nominate up to three staff per test site as systems navigators and/or counselors. Similar to HPTN 074, the roles of navigators and counselors may be performed by a single person or two distinct persons at the discretion of the test site.

We will conduct regional (north, south, central) trainings for navigators and counselors for all study test sites to ensure that SNaP training is uniform across study arms *prior to* notifying the sites of their SA/TA allocation.

The 2-day, in-person training will be conducted by the centralized training team and rely heavily on the training manual developed for HPTN 074, which will be minimally modified for use at scale. The training will include introduction to motivational interviewing, counseling techniques practices, and a series of guided role play activities, in which real-time feedback will be provided by the training team. Any new navigators or counselors will be trained similarly. Refresher trainings will be held annually.

- **Training on seek strategies:**

At the regional training, implementation teams will provide strategies to reach out to PWID in their catchment area. Strategies will include communicating with needle exchange sites, MAT clinics and other substance use treatment centers (including mandatory 06/07 detoxification centers). The goal is to ensure active referrals of MAT patients to HIV test sites and provide information cards about HIV testing to PWID to distribute in their networks. These strategies were used to effectively “seek” PWID in HPTN 074.

- **Training on implementation strategies for SA and TA:**

During or immediately after the navigator/counselor regional training, a 2-day regional training will be held for all test sites to introduce the project, orient to common implementation barriers and facilitators across sites, and train teams on the SA implementation package. TA implementation teams will subsequently visit each TA site in the region to conduct trainings on site-specific implementation strategies.

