### 5.2.1 Central Implementation Teams (see also Section 4.2)

As stated in Section 4.2, distinct central implementation teams (one for each arm) will facilitate study implementation. Each implementation team will comprise:

- 1) A UNC-Vietnam Hanoi staff member,
- 2) A VAAC representative, and
- 3) An HMU representative.

Implementation will be done for both arms simultaneously in a rolling process, working systematically through the regions of Vietnam. Central implementation teams will have separate group calls with the SA and TA test sites every 6 months to share experiences and lessons learned.

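### Masking of fidelity quality raters to arm (7.2.1) is not supported by the design as described: the named raters are the arm-specific central implementation teams

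*Combined protocol and SAP*

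**What the plan says.** All references are to the combined protocol and SAP.

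- **Masking.** Section 7.2.1: "Reviewers will be masked to the arm when reviewing navigation forms or audio-recordings". No procedure follows.
- **Who rates.** Section 5.6.1: "the central implementation teams will review the first 10 navigation encounter forms", plus a random half of the rest, on a 5-point scale. Section 5.6.2: "the central implementation teams will also review the first 5 counseling session audio-recordings", plus a random half of the rest, on a 10-point scale. Section 7.2.1 also names the central implementation team as scorer.
- **Who the teams are.** Section 4.2: "After randomization, two central implementation teams (one for each arm) will facilitate study implementation". Section 5.2.1 repeats it: "distinct central implementation teams (one for each arm) will facilitate study implementation".
- **Contact with sites.** Section 5.1.6: "TA implementation teams will subsequently visit each TA site in the region to conduct trainings on site-specific implementation strategies". Section 4.2.2 adds three one-hour coaching sessions for each TA site, monthly calls and re-training by the TA team. Section 4.2 provides group calls every six months, held separately for TA and standard-approach (SA) sites.
- **What is concealed.** Section 5.6.2, for central review of recordings: "identifying information of the PWID will not be provided to the central team". Nothing is said about site, navigator, counselor or arm identity, or about how material is assigned to reviewers.
- **Flow of material.** Section 5.6 sends the navigation and counseling encounter forms to Hanoi every month for data entry. Section 5.6.2 adds: "The quality rating forms and recordings will be forwarded monthly to the Hanoi team".
- **Use of the rating.** In Section 7.2.1 the average quality rating multiplies the completion percentage, separately for navigation and counseling, and the two products are added (range 0 to 200).

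**The concern.** The plan claims a property, masking to arm, for a subjective rating, then assigns the rating to people whose role after randomization is defined by arm. A member of the TA team who has trained and coached a site knows its arm as soon as the site, navigator or counselor can be recognized on a form or in a recording. Withholding the PWID's identity does not prevent that.

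Quality multiplies completion in both halves of the score, so a difference in rating between arms passes straight into the comparison on a primary outcome. Section 4.2 also states an expectation that the tailored condition will do better, which is the usual reason to want masked raters. The same score feeds the threshold of 136 that helps define successful sites for Aim 3 (Sections 5.4 and 7.5).

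The exposure is limited. ART uptake, the other primary outcome, comes from clinic records, and session completion comes from logs. Neither uses these ratings.

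**Working it through.** **1. The text.** Three statements have to hold together: reviewers are masked to arm (7.2.1); reviewers are the central implementation teams (5.6.1, 5.6.2, 7.2.1); those teams are distinct, one per arm, with the TA team in regular contact with every TA site (4.2, 4.2.2, 5.1.6, 5.2.1). They are compatible only if site, staff and arm are concealed in the rated material. Crossed review alone would not be enough, since a reviewer who recognizes the site knows the arm. The documents describe concealment of the PWID only, and state it for recordings only.

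**2. The plan's own power (8.1.1).** Inputs: 21 sites per arm, two-sided alpha 0.05, site as unit, t test with 40 df. The standard error of the difference is SD × √(2/21): 12.34 at SD 40 and 8.64 at SD 28.

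- 136 − 100.5 = 35.5; 35.5/12.34 = 2.88; power 80.1%.
- 136 − 111 = 25; 25/8.64 = 2.89; power 80.6%.

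Both reproduce the stated 80%.

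**3. What a rating differential would do.** With completion proportions cN (navigation) and cC (counseling), and an assumed differential b in quality between arms on both instruments, the shift in fidelity is 100 × (cN + cC) × b. With no true difference, the rejection rate comes from the noncentral t with 40 df and noncentrality shift/(SD × √(2/21)).

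| Completion | Assumed b | Shift | Type I error, SD 40 | Type I error, SD 28 |
|---|---|---|---|---|
| 80%/80% | 2 points | 160 × 0.02 = 3.2 | 5.7% | 6.5% |
| 75%/75% | 5 points | 150 × 0.05 = 7.5 | 9.1% | 13.5% |
| 80%/80% | 5 points | 160 × 0.05 = 8.0 | 9.7% | 14.8% |
| 90%/80% | 5 points | 170 × 0.05 = 8.5 | 10.3% | 16.0% |
| 80%, one instrument only | 5 points | 80 × 0.05 = 4.0 | 6.2% | 7.4% |

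The completion values are those in Sections 7.2.1 and 8.1.1. The values of b are assumptions. The documents do not define how scale scores become percentages. If it is score divided by maximum, one step is 20 points on the navigation scale and 10 on the counseling scale, so 5 points is a quarter-step and a half-step.

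**4. Rating volume**, for the cost of the fix, with two navigation sessions and one counseling session per PWID, an assumed 80% completion, and 42 sites.

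- 6200 PWID: 9920 navigation forms, of which 420 + 0.5 × (9920 − 420) = 5170 are rated; 4960 recordings, of which 210 + 0.5 × (4960 − 210) = 2585 are rated.
- 7035 PWID (the Section 3.5.1 figure before mortality): 420 + 0.5 × (11256 − 420) = 5838 forms; 210 + 0.5 × (5628 − 210) = 2919 recordings.

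Extra sessions would add to these counts; refused consent to recording would reduce them.

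**The case against.** The strongest reply is that this is missing detail rather than a contradiction. Section 7.2.1 commits to masking outright. The sections that create arm-specific teams give them the task of facilitating implementation and do not say that each rates its own arm. Sections 5.6.1 and 5.6.2 use the plural, teams, which fits pooled or crossed review. Sections 5 and 12.2 leave detailed procedures, including forms processing, to SOPs outside these documents. Encounter forms already pass through Hanoi, where coding could take place. All of this stands, and it limits the finding to a masking claim without visible support.

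Three stronger readings are tempting, and the documents support none of them.

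- **That raters are unmasked, or that each team scores only its own arm.** No section says so, and the masking rule speaks against it.
- **That fidelity will be biased toward TA.** The documents give neither size nor direction for a rating difference. The 9% to 16% type I error figures require a constant 5-point differential in every site on both instruments; at 2 points the effect is small.
- **That exposure to bias equals the share of the planned difference owed to quality.** That share describes the hoped-for true effect. The shift from biased rating depends only on completion and on the size of the bias.

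The objection does not dispose of the point. A masking property claimed for a component of a primary outcome needs a described or cited procedure, and the one concealment step given does not address arm.

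**Conclusion.** The concern holds in a limited form: the masking stated in Section 7.2.1 is unsupported by the raters and the de-identification that the plan describes, but it is not shown to have failed. Confidence is high that the text lacks a supporting procedure; nothing can be concluded about actual bias. The illustrative size, 9.7% to 14.8% type I error for a 5-point differential on both instruments at 80% completion, rests wholly on that assumed differential and on the planned SDs of 40 and 28. This should be fixed. It does not invalidate the trial, because ART uptake and session completion do not depend on the ratings.

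**What to change.** In Sections 5.6 and 7.2.1, state the following, or cite the SOP that already does:

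1. Site, staff and arm identifiers are removed from navigation forms and recording labels before rating. The monthly transfer of encounter forms to Hanoi could host this step, with the allocation key held by data staff who do not rate.
2. Sampled material from all 42 sites is allocated at random across the existing reviewers of both teams, so that each reviewer scores both arms in equal share. Reviewer identity is recorded.
3. The Section 7.2.1 score and the 136 threshold stay as they are.
4. Section 8.2.1 adds two sensitivity analyses: a quality score adjusted for reviewer as a fixed effect, and completion alone. Note that completion comes from logs kept by site staff who are not masked.

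The rolling trial calendar and the post-completion work in Version 3.0 suggest that much rating may already be done; this is an inference. If so, report who rated which arm and re-rate a random subset under masking where feasible. If crossed, masked rating cannot be done, withdraw the masking statement.

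**Cost.** Same reviewers, same number of ratings, same primary score. The work is coding and logging roughly 5,200 to 5,800 forms and 2,600 to 2,900 recordings, possibly sending recordings to Hanoi before rather than after rating, and any re-rating.

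**Limits.** Voices may still unmask some recordings, and the protocol should say so. Crossing cancels a general difference in severity between teams, but leniency toward a reviewer's own arm is reduced rather than removed. With equal shares, a one-sided 5-point leniency that survives masking becomes 2.5 points: a shift of 160 × 0.025 = 4.0 and type I error of 6.2% to 7.4%. The reviewer adjustment may not detect it.
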